#### **Phase 4 (visit 2):**

**Purpose:** to assess ambulatory efficacy and lifetime of the microprobe array sensor over 5 days in continuous ISF glucose monitoring in comparison to iPro2 in 20 subjects with type 1 diabetes

#### **Primary outcome:**

- Correlation with ISF CGM (iPro2 – Medtronic)

#### **Secondary outcomes:**

- Clarke error grid
- Skin inflammation
- Pain score
- Acceptability questionnaire
- Magnitude of current

#### **Visit:**

- On the morning of the visit, subjects will be instructed to have their standard breakfast and to adhere to their usual practice of diabetes management; this will be maintained throughout the study period.
- Attend the Wellcome Trust-Sir John McMichael Clinical Research Facility at the Hammersmith Hospital campus of Imperial College between 9:00 - 10:00 am
- Between 10:00 – 11:00, microprobe array and iPro2 device will be implanted in each subject.
- The outer margin of a 2 cm^2 skin area on the ventral aspect of the non-dominant forearm will be marked before the application of sterile microprobe array to the center of this skin area. The marked skin area will be shaved if hairy. Microprobe insertion will be achieved by applying gentle pressure. Microprobe array will be secured in place using adhesive plaster for 24 hours with 5 minutes sampling as moving average of 1 minute intervals.

- Medtronic iPro2 (Northridge, California) retrospective/blinded continuous glucose monitoring sensor will be implanted in the anterior abdominal wall and calibrated as per manufacturer's instructions.
- Subjects will be allowed to go home with advice to have normal daily activity with no alteration to their insulin doses or other aspects of diabetes management. Subjects will be asked to keep a food diary and a diary for self-monitored blood glucose levels.
- Subjects will attend the research unit on day 6 between 9:00-10:00. The 2 devices will be removed. Skin area around the microprobe array will be inspected by a doctor for any evidence of skin inflammation using a 4-point scale (none, mild, moderate and severe). This will be compared to skin area around iPro2 sensor insertion site.
- Following removal of the device, the microprobe treated skin area will be examined using confocal microscopy imaging technique to confirm penetration and examine the created microchannels.
- Microprobe arrays will be examined for integrity before and after application using SEM.
- Visual analogue scale (VAS) will be used to assess pain resulting from microprobe insertion in comparison with pain resulting from blood sampling and pain resulting from insertion of iPro2 sensor.
- At the end of the 5 days ambulatory period, subjects will be asked to fill a validated acceptability questionnaire.

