#### 4. Trial Objectives and Purpose

This trial assesses the safety and efficacy of the Imperial Microprobe array biosensor for continuous monitoring of ISF glucose.

Safety will be assessed in relation to skin inflammation, skin damage, risk of fracture of microprobe tips within skin layers and pain. This will be assessed over six hours initially then over 24 hours in non-diabetic volunteers then over 24 hours in subjects with type 1 diabetes as in-patients and finally, in ambulatory situation over 5 days.

Efficacy will be assessed mechanically (ability to penetrate stratum corneum) and functionally (ability to sense ISF analytes). Functional efficacy of microprobe arrays to continuously monitor ISF glucose will be assessed in comparison to venous blood glucose levels and ISF glucose using iPro2 in as inpatients (phase3) then in an ambulatory state (phase 4).

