### **Phase 3:**

**Purpose:** to assess safety and efficacy of the device over 24 hours in comparison to venous blood glucose and interstitial fluid (ISF) glucose using iPro2 in 20 subjects with type 1 diabetes as inpatients.

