#### **Visit 1:**

- On the morning of the visit, subjects will be instructed to have their standard breakfast and to adhere to their usual practice of diabetes management, this will be maintained throughout study period.
- Attend the Wellcome Trust-Sir John McMichael Clinical Research Facility at the Hammersmith Hospital campus of Imperial College between 9:00 - 10:00 am.
- Between 10:00 – 11:00; subjects will undergo routine clinical examination, have venous blood taken for HbA1c, lipids, creatinine, liver function tests, FBC following an intravenous cannula insertion and female subjects of childbearing age will have a urine pregnancy test performed. This will be followed by insertion of microprobe array and iPro2 device in each subject.
- The outer margin of a 2 cm^2 skin area on the ventral aspect of the non-dominant forearm will be marked before the application of sterile microprobe array to the center of this skin area. The marked skin area will be shaved if hairy. Microprobe insertion will be achieved by applying gentle pressure. Microprobe array will be secured in place using adhesive plaster for 24 hours with 5 minutes sampling as moving average of 1 minute intervals.
- Medtronic iPro2 (Northridge, California) retrospective/blinded continuous glucose monitoring sensor will be implanted in the anterior abdominal wall and calibrated as per manufacturer's instructions.
- An 18-G intravenous cannula will be inserted in the non-dominant upper limb for venous sampling. 2.5 mL venous blood will be taken at 30 minutes intervals between 11:00 - 22:00 the at 60 minutes intervals between 22:00 – 7:00 then back to 30 minutes intervals between 7:00 – 11:00. Venous blood samples will be distributed for venous blood glucose using YSI analyser. Thus, in total, 40 venous samples will be withdrawn from each subject. Maximum blood volume collected over study visit duration is 100mL.
- A 60g CHO meal will be provided between 12:00 – 13:00.
- A 20 g CHO snack will be provided between 15:00 – 16:00 (optional).
- A 60 g CHO meal will be provided between 18:00 – 19:00.
- A 20 g CHO snack will be provided between 22:00 – 23:00 before sleep (optional).
- A 40 g CHO meal will be provided between 7:00 – 8:00.
- At 11:00, devices and intravenous catheter will be removed.

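### The Phase 4 visit instruction secures and samples the array for 24 hours, but Phase 4 is a 5-day study with removal on day 6

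*Protocol*

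**What the plan says.** All references are to the Protocol.

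- **Section 5, Phase 4, Visit.** The array is to be "secured in place using adhesive plaster for 24 hours with 5 minutes sampling as moving average of 1 minute intervals". No other securing or sampling duration is given for the Phase 4 array.
- **Same visit list, start and end.** "Between 10:00 – 11:00, microprobe array and iPro2 device will be implanted in each subject"; later, "Subjects will attend the research unit on day 6 between 9:00-10:00. The 2 devices will be removed". The acceptability questionnaire follows at the end of a five-day ambulatory period.
- **Section 5, Phase 4, Purpose.** "to assess ambulatory efficacy and lifetime of the microprobe array sensor over 5 days", compared with iPro2 in 20 subjects with type 1 diabetes. The primary outcome is correlation with iPro2.
- **Section 4.** Safety is to be assessed in stages ending "finally, in ambulatory situation over 5 days".
- **Section 5, Phase 3.** The securing and sampling sentence is word for word the same. The purpose there is "to assess safety and efficacy of the device over 24 hours in comparison to venous blood glucose", and the visit ends the next day: "At 11:00, devices and intravenous catheter will be removed".

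**The concern.** The Phase 3 sentence appears to have been carried into Phase 4 without changing the duration, although the document does not prove that origin. In Phase 3 it agrees with the purpose and the removal time. In Phase 4 it agrees with neither.

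The sentence is an operative instruction, so staff may act on it. If they did, array data would end after day 1. The correlation with iPro2 could still be computed, but only over the recording length that Phase 3 already supplies. Phase 4 is the only phase planned beyond 24 hours and the only one that names sensor lifetime as a purpose, so no other part of the trial could make good the loss. Subjects go home after insertion and no visit is scheduled before day 6, so a recording that stopped early would not be noticed at a visit in time to rescue that subject's data.

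**Working it through.** **1. The Phase 4 durations side by side**

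| Place in the Protocol | Duration stated or implied |
|---|---|
| Section 4 (safety) | 5 days |
| Phase 4 purpose (efficacy and lifetime) | 5 days |
| Phase 4 visit, removal of both devices | day 6 |
| Phase 4 visit, questionnaire | end of 5 days |
| Phase 4 visit, securing and sampling | 24 hours |

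Two other time spans are not counterexamples. The twenty-four-hour period in Section 8 is explicitly an in-patient period, which is Phase 3. The 12 to 18 months in Section 7 is the participation window for Phases 3 and 4, not device wear.

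**2. Could 24 hours be deliberate?** The Phase 4 visit list has no step at 24 hours that removes the array, renews it or stops recording. Where the protocol wants sampling to be shorter than wear it says so: in Phase 2 the array stays on for 24 hours and sampling is limited to the first six. Phase 4 has no such limit.

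**3. Does the stated figure follow from the schedule?** Wear = removal time − insertion time.

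- Shortest: day 1 at 11:00 to day 6 at 09:00 = 5 × 24 − 2 = 118 hours.
- Longest: day 1 at 10:00 to day 6 at 10:00 = 5 × 24 = 120 hours.

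The stated 24 hours cannot be obtained from the Phase 4 schedule. It does match Phase 3, where the devices come out at 11:00 the next day.

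**4. Readings per subject.** One reading every 5 minutes is 12 per hour.

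- Planned schedule: 118 × 12 = 1,416 to 120 × 12 = 1,440.
- Literal instruction: 24 × 12 = 288.
- Share recorded: 288/1,416 = 20.3% to 288/1,440 = 20.0%.
- Unrecorded: 118 − 24 = 94 hours to 120 − 24 = 96 hours.

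**5. Across the phase.** The protocol does not define a visit cycle, so the number of subjects affected before a review noticed cannot be derived. The assumed range runs from one subject to all 20.

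- One subject: 94 to 96 hours lost.
- All 20: planned 20 × 118 = 2,360 to 20 × 120 = 2,400 subject-hours; recorded 20 × 24 = 480; lost 1,880 to 1,920.

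These are shares of recording time. They are not shares of statistical information, because readings within a subject are serially dependent.

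**The case against.** The best defence is that the text largely corrects itself. An array removed on day 6 cannot have come off at 24 hours, and the phase purpose leaves no doubt about the intended length. The 24 hours can also be read as attached only to the adhesive securing, with the sampling clause giving a frequency and no duration. Phase 2 lends support, since sampling gets its own limit there when it is meant to be shorter than wear. On that reading the text never orders recording to stop, and the comparison of 288 with 1,416 readings does not arise. Nor does the protocol describe a recorder setting that would end sampling at 24 hours while the subject is at home. Finally, no sample size, power figure or analysis rule depends on the phrase, because Section 10 contains no power calculation.

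Much of this stands. The intended value is recoverable, the loss figures hold only under literal execution, and the weekly meetings, monthly data reviews and end-of-cycle review in Section 20 could catch the problem for later subjects. The grammatical reading does not remove the error, however. Securing for 24 hours still contradicts removal on day 6, and an array secured for one day does not support five days of recording.

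**Conclusion.** The concern holds. The Phase 4 visit instruction states a wrong duration, contradicted by the objectives, the phase purpose and two other steps in its own list.

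The worst case for a subject is 94 to 96 of 118 to 120 hours without array data, leaving about 20% of the planned recording time. This assumes that the 24 hours governs sampling as well as securing and that staff follow it literally. If they record until the day-6 removal, nothing is lost.

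It should be fixed because the phrase sits in an operative instruction and bears on the purpose that only Phase 4 serves. It does not undermine the design, and the primary correlation remains computable either way.

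**What to change.** In Section 5, Phase 4, Visit, replace the 24-hour phrase with: from insertion until device removal on day 6 (5 days). Word it so that the duration plainly covers both the securing of the array and the 5-minute sampling. The identical sentence in Phase 3 is correct and should stay.

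The cost is one phrase. Removal on day 6 is already planned, so no visit, procedure or sample-size change follows.

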## 6. Methodology

Non-randomised open label study

## 7. Timescale

It is anticipated that the studies will take place over 4 years. Non-diabetic subjects will be recruited to the study for phase 1 and 2 (2 visits). Subject with type 1 diabetes will be recruited for phases 3 and 4 of the study for up to 12 - 18 months, with a total of 2 visits in that timeframe.

**8. Potential risks and benefits** The potential risks and burdens for research participants are as follows:

Skin inflammation may occur with the use of microprobe arrays. A literature review shows this to be minimal and transient. Subjects will be examined regularly by a doctor to assess the degree of any inflammatory reaction and the need for any intervention (ending the study or the use of local/systemic therapy if required).

Pain may result from microprobe array insertion. A literature review shows this to be absent or very minimal when compared to traditional needles or lancets. The array will be inserted with gentle manual pressure and pain score will be assessed in phases 2, 3 and 4.

In all visits (excluding phase 4) there is either a venous blood test or insertion of an intravenous cannula. These have the potential to cause discomfort. This will be minimised by experienced research personnel performing the procedure and appropriate use of equipment and aseptic technique.

In phases 3 and 4, subjects will have a continuous glucose-monitoring sensor (iPro2, Medtronic) inserted in anterior abdominal wall subcutaneous tissue. Sensor insertion can be associated with some discomfort but the insertion devices are spring-loaded with introducers, making the process rapid and often painless. Any discomfort will be minimised by adhering to manufacturer's instructions.

Assessment of efficacy of the device will be in comparison to venous glucose levels and a commercially available continuous glucose sensor over a period of twenty-four hours as in-patients. 2.5 mL venous blood will be taken at 30 minutes intervals apart from the period between 11:00 - 22:00 when the blood will be taken hourly.

During studies involving subjects with type 1 diabetes, subjects will adhere to their usual practice of diabetes management.

It is acknowledged that the clinical schedule is demanding of subject's time. This will be made clear prior to consent. This inconvenience is necessary to adequately and safely validate the device and we will minimise the burden as much as possible by providing entertainment (TV, radio, reading material, internet access) in a comfortable environment with privacy. We will also ensure make every effort to schedule visits around subject's lifestyles.

Research participants will benefit from being in the study by having increased access to diabetes professionals and more frequent visits to hospital with an emphasis on improved glycaemic control.

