#### **Secondary outcomes:**

- Clarke error grid
- Skin inflammation
- Skin penetration
- Pain score
- Acceptability questionnaire
- Magnitude of current

**Subject inclusion criteria** Subjects may be recruited if:

- Adults over 18 years of age
- Diagnosed with Type 1 diabetes for greater than 1 year
- HbA1c less than or equal to 9.0 % (75 mmol/mol)
- Registered with a GP

**Subject exclusion criteria** Subjects are excluded if:

- History of diabetic dermopathy or pre-existing skin condition
- History of upper limb neuropathy or radiculopathy
- Pregnant or planning pregnancy in next 12 months
- Breastfeeding
- Enrolled in other clinical trials
- uncontrolled concurrent illness
- physical or visual impairment preventing sensor's use
- Have active malignancy or under investigation for malignancy

**Subject withdrawal criteria** Subjects will be withdrawn from the study in the case of:

1. Loss of capacity to give informed consent
2. Development of diabetic neuropathy, dermopathy or other skin conditions
3. Terminal illness

Withdrawal will be immediate and subjects will be followed up in the appropriate out-patient diabetes clinic within 4 weeks of withdrawal.

Recruiting will be undertaken in the diabetes clinics at St. Mary's Hospital and Charing Cross Hospital campuses of Imperial College Healthcare NHS Trust. Participant information sheets will be given to

potential subjects and, after a minimum of 48 hours and following any questions, informed consent will be taken.

Usual care will be maintained for diabetes throughout the study. No concomitant medical therapies are contra-indicated.

Subjects will be asked not to apply any cosmetic formulations on the non-dominant forearm for 7 days prior to the study.

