- Skin area around the microprobe array will be inspected at 1, 2, 6 hours post-insertion and after removal of the device at 24 hours by a doctor for any evidence of skin inflammation using a 4-point scale (none, mild, moderate and severe). This will be compared to skin area around iPro2 sensor insertion site.
- Following removal of the device at 24 hours, the microprobe treated skin area will be examined using confocal microscopy imaging technique to confirm penetration and examine the created microchannels.
- Microprobe arrays will be examined for integrity before and after application using SEM.
- Visual analogue scale (VAS) will be used to assess pain resulting from microprobe insertion in comparison with pain resulting from blood sampling and pain resulting from insertion of iPro2 sensor.
- At the end of the 24 hour period, subjects will be asked to fill a validated acceptability questionnaire.

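### Section 8 relies on regular examination by a doctor against skin inflammation, but Phase 4 plans no skin observation during 118-120 h of home wear and a single grade after removal

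*Protocol*

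**What the plan says.** Section 8 lists skin inflammation first among the risks and answers it with "Subjects will be examined regularly by a doctor to assess the degree of any inflammatory reaction and the need for any intervention". The interventions it names are ending the study and giving local or systemic treatment. The statement is not limited to any phase, although the same section does limit other statements by phase: it excludes Phase 4 for venous procedures and names Phases 2, 3 and 4 for pain scores.

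Section 4 makes skin inflammation and skin damage safety objectives, ending with five days of ambulatory use.

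Section 5 sets the schedule. In Phase 3 the skin is "inspected at 1, 2, 6 hours post-insertion and after removal of the device at 24 hours". In Phase 4, insertion is between 10:00 and 11:00 on day 1, after which subjects go home. The next contact described is: "Subjects will attend the research unit on day 6 between 9:00-10:00. The 2 devices will be removed". A doctor then grades the skin once, on the four-point scale, and compares it with the iPro2 site. For the days at home, "Subjects will be asked to keep a food diary and a diary for self-monitored blood glucose levels". No skin entry, interim contact or self-check is described.

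**The concern.** Section 8 gives the examination a purpose: a doctor judges whether to intervene. An examination made only after the device has come off cannot inform a decision to take it off early. Phase 4 is also the first time anyone wears the array for more than 24 h, so experience from the earlier phases does not cover most of it.

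Two things are at stake. One is participant protection, if a reaction worsens at home. The other is ascertainment for the five-day skin-safety objective: a single grade at the end of wear misses any reaction that has already settled, and Section 8 itself expects inflammation to be transient.

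**Working it through.** The protocol states no figure to reproduce. The check is a count of scheduled inspections and a calculation of wear time from the clock times in Section 5.

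**Doctor skin inspections by phase**

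| Phase | Planned wear | During wear | After removal | Total |
|---|---|---|---|---|
| 1 | 6 h | 2 (1, 2 h) | 1 | 3 |
| 2 | 24 h | 3 (1, 2, 6 h) | 1 | 4 |
| 3 | 24 h | 3 (1, 2, 6 h) | 1 | 4 |
| 4 | 5 days | 0 | 1 | 1 |

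**Phase 4 wear time**

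- Day 1 to day 6 at the same clock time: 5 × 24 = 120 h.
- Shortest, inserted 11:00 and removed 9:00: 120 − 2 = 118 h.
- Longest, inserted 10:00 and removed 10:00: 120 h.

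**Wear beyond any earlier exposure** (longest earlier wear 24 h)

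- Shortest: 118 − 24 = 94 h; 94/118 = 79.7%.
- Longest: 120 − 24 = 96 h; 96/120 = 80.0%.

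**Longest interval without a planned inspection**

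- Phases 2 and 3: from 6 h to 24 h, which is 18 h. Phase 3 subjects are in-patients throughout.
- Phase 4: the whole of wear, 118 to 120 h.

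**Checks per subject across Phases 3 and 4.** The Phase 4 heading begins "Phase 4 (visit 2", and Section 7 says "Subject with type 1 diabetes will be recruited for phases 3 and 4 of the study", with two visits in all. If these are the same people, each has 4 + 1 = 5 doctor checks, none of them between hour 24 of wear and removal.

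**Other provisions that might fill the interval**

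- Section 20: the management team reviews data when a visit cycle ends and again before the next begins. This controls progression to longer wear but does not observe skin during wear.
- Section 9: cites the duty to record all adverse events. It would capture what a subject reports but describes no way of asking.
- Section 14: the right to withdraw is general.

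None of these provides an observation during Phase 4 wear.

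**The case against.** The strongest reply is that Section 8 is a general risk statement. It gives no frequency for the examinations and does not promise one during home wear. Five doctor checks over two visits could fairly be called regular, and the protocol already accepts home wear without inspection in Phase 2, from 6 h to about 24 h. This stands as far as it goes: a reader might infer that Section 8 and Phase 4 flatly contradict each other, and the text does not support that. It does not answer the point that an examination meant to guide intervention is planned only after wear has ended.

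Three other stronger readings also fail.

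- A reader might conclude that a transient reaction would go unrecorded. Section 9 would cover one that the subject mentions on day 6. What is missing is a planned grade.
- A reader might treat any site reaction as meeting the Phase 3 withdrawal criterion, "Development of diabetic neuropathy, dermopathy or other skin conditions", which carries immediate withdrawal. Site inflammation is an outcome graded from none to severe, and Section 8 leaves the response to a doctor. If any reaction triggered withdrawal, a mild grade at 1 h in Phase 3 would end participation.
- A reader might infer that subjects are never told to report a reaction. The participant papers are not shown and may well tell them.

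Two mitigating facts also stand. On the two-visit reading, reactions in the first 24 h will have been looked for in the same people in Phase 3. The Section 20 review also comes before the move to longer wear. Neither reaches hours 24 to about 120.

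**Conclusion.** The point holds as a gap in delivering a stated safeguard. Phase 4 plans no skin observation in 118 to 120 h of home wear, of which 94 to 96 h (about 80%) exceed any earlier exposure, in all 20 planned subjects. The single planned grade comes after removal. The weight is limited: skin inflammation is secondary in Phase 4, and no primary outcome or sample size is affected. The documents do not say how often a reaction would occur in these hours, and no estimate is offered.

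The conclusion assumes that five-day wear is intended. The Phase 4 visit text also says "Microprobe array will be secured in place using adhesive plaster for 24 hours", but the stated five-day purpose, the day-6 removal of both devices and the questionnaire after five days indicate that this wording was carried over from Phase 3. The count of five checks per subject further assumes that Phase 4 uses the Phase 3 subjects; the absence of observation during Phase 4 wear does not depend on that.

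**What to change.** 1. Add a daily line to the diary that Phase 4 subjects already keep: none, mild, moderate or severe, for the visible skin around the array and around the iPro2 site, without lifting the plaster. Days 2 to 5 give 4 entries per subject, or 4 × 20 = 80 in all.
2. Unless the participant papers already say so, instruct subjects to contact the study team about a moderate, severe or worsening reaction, so that a doctor can judge the need for intervention or early removal under Section 8. Do not apply the automatic withdrawal rule to site reactions; doing so could remove subjects for mild redness and cut short the sensor data behind the primary outcome.
3. Report the worst self-grade separately from the doctor's day-6 grade.
4. Amend Section 8 to say that Phase 4 relies on self-report during wear plus one examination by a doctor at removal.

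This is a cheap improvement: one diary line, one instruction and one sentence, with no extra visit. Its limits should be stated: self-grades are less reliable than a doctor's, and the plaster may hide part of the site, so an entry of none covers only the skin that can be seen.
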